Enrollment	Point/time of patient entry into the study; the point at which informed consent must be obtained (i.e. prior to starting any of the procedures described in the protocol)
Investigational drug	The study drug whose properties are being tested in the study; this definition is consistent with US CFR 21 Section 312.3 and is synonymous with "investigational new drug."
Medication number	A unique identifier on the label of each medication package in studies that dispense medication using an IVR system
Patient number	A number assigned to each patient who enrolls in the study. When combined with the center number, a unique identifier is created for each patient in the study.
Stage	A major subdivision of the study timeline; begins and ends with major study milestones such as enrollment, randomization, completion of treatment, etc.
Period	A minor subdivision of the study timeline; divides phases into smaller functional segments such as screening, baseline, titration, washout, etc.
Premature patient withdrawal	Point/time when the patient exits from the study prior to the planned completion of all study drug administration and assessments; at this time all study drug administration is discontinued and no further assessments are planned
Randomization number	A unique identifier assigned to each randomized patient, corresponding to a specific treatment arm assignment
Stop study participation	Point/time at which the patient came in for a final evaluation visit or when study drug was discontinued whichever is later
Study drug	Any drug administered to the patient as part of the required study procedures; includes investigational drug and any control drugs
Study drug discontinuation	Point/time when patient permanently stops taking study drug for any reason; may or may not also be the point/time of premature patient withdrawal
Variable	Information used in the data analysis; derived directly or indirectly from data collected using specified assessments at specified timepoints

Protocol synopsis

Title of study: A prospective, randomized, single center pilot study comparing patient and graft survival, adverse events and tolerability of Zortress® (everolimus) versus Rapamune® (sirolimus) in combination with low dose Neoral® (cyclosporine) dosed by C2 monitoring, in deceased and living donor renal transplant recipients under a Thymoglobulin® (antithymocyte globulin) and rapid steroid induction protocol.

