Potential study participants will be approached for consent immediately prior to transplantation by the transplant surgeon or appointed representative if they meet the inclusion criteria above and do not fit the exclusion criteria above. If the transplant candidate agrees to participate he/she will be categorized as a living or deceased donor kidney recipient category and as primary or subsequent kidney transplant recipient. The candidate will then be randomized, in a 2:1 fashion, to either the Zortress or Rapamune study arm. Following transplantation all recipients will receive daily Thymoglobulin doses of 1.25 mg/kg starting on POD #1 for 4 to 5 doses adjusted for white blood count and platelet count. All recipients will be administered steroids as methylprednisolone IV for two doses, then oral prednisone at: 500 mg, 200 mg, 125 mg, 50 mg, and 25 mg and will receive delayed Neoral® on POD #2-3 dosed to achieve serum levels of 800 to 1000 ng/ml by immunoassay until 3 months post-transplant, 600-800 ng/ml 3-6 months post-transplant, 400-600 ng/ml 6-12 months post-transplant, and 400 ng/ml > 12 months post-transplant. Zortress® will be started on POD #0 for Zortress study arm recipients, administered bid and dosed to achieve target levels of 3 to 8 ng/ml by approved testing methods; Rapamune® study arm recipients will receive Rapamune once daily, dosed to achieve target levels of 10 to 18 ng/ml by Architect assay, or 8 to 12 by LC-MS methodology. Neoral and Rapamune/Zortress levels will be monitored twice weekly for the first 3 months, once weekly for months 3-6, every other week months 6-12, and monthly thereafter. This pilot study is estimated to take one year for enrollment and three years from the date of last patient enrollment for completion of last patient visit, then several months for completion of paper work. This will be about 4.5 to 5 years.

Efficacy assessments:

- Incidence of graft loss in the first post-transplant year
- Incidence of patient death in the first post-transplant year
- Incidence of acute rejection at 1 year post-transplant

Other assessments:

- Incidence of non-death censored graft loss at 6 months, 2 and 3 years after transplantation
- Number and grade of acute rejection episodes at 6 months, 1, 2, and 3 years after transplantation
- Tolerability of Zortress at 1 year post-transplant
- Estimated GFR at 6 months, 1, 2, and 3 years after transplantation
- Incidence of CMV, EBV and BK infections 1 year after transplantation

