3.3 Exploratory objectives

4 To explore the kidney and vascular endothelial function assessed by a panel of molecular markers over the observation period. Study design

Randomized, single center parallel-group, open-label study.

Pilot study with exploratory objectives.

Eligibility: All primary or retransplant recipients of deceased donor or living donor grafts with negative crossmatch who are felt to have good expectations for renal function recovery after surgery will be offered entry into the study.

Treatment scheme is as described above, with Solumedrol 500 mg IV in OR as induction, then 5 doses of Thymoglobulin starting morning of POD 1 at 1.25 mg/dose (rounded to nearest 25 mg) with rapid steroid taper over five doses. The mTOR inhibitor drug will be started on POD 0 and Neoral introduced as renal function recovers, usually starting on POD 2.

Measurement/Assessments: as described above, graft and patient survival per standard definitions, clinically indicated biopsies for determination of acute cellular or antibody mediated rejection, renal function as estimated from serum Cr based on MDRD, clinic visits for wound assessment, standard of care labs for renal function, bone marrow function (WBC and platelet count), liver function, lipid panel, donor specific antibody determination during any significant increase in serum Cr, drug levels routinely monitored for need of number of dose adjustments and compliance, Emergency Room and hospitalizations, as well as unscheduled clinic and other physician visits. For the pilot study, we would perform scheduled CMV, EBV and serum BK PCRs monthly for the first year, then quarterly or with any viral symptoms.

A subset of patients will have coded plasma samples sent to clinical research and development at the University of Colorado. These biomarker samples will be used to assess vascular endothelial dysfunction and inflammation markers as well as kidney dysfunction markers.

Plasma samples are collected and stored at The Ohio State University Wexner Medical Center tissue typing lab per standard of care.

5 Population

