10.1.2 Statistical hypothesis, model, and method of analysis

The primary endpoint will be a composite endpoint of graft survival (non-death censored) and biopsy proven acute rejection at 1 year.

Secondary endpoints at 6 months, 1, 2 and 3 years will include: graft survival and patient survival/death at 2 and 3 years, rate and grade of acute cellular rejection, rate of acute antibody mediated rejection, rate of new donor specific antibody formation, estimated CrCl by MDRD, lipid control as determined by requirement for anti-lipid medications and average levels with and without medications, ability to maintain initial immunosuppressive medications and reason for switch if required, wound complications as determined by need for wound packing, infection treatment with antibiotics, presence of hernia on exam and requirement for hernia repair, as well as presence of symptomatic lymphocele, and New Onset Diabetes After Transplant as determined by need for new oral or sustained Insulin medication.

Statistical analysis will be performed on SPSS or STATA software with dichotomous variables evaluated by Chi-Squared analysis, continuous variables by Student's T-Test, non-parametric outcomes will be assessed by Wilcoxon rank sum test (Mann-Whitney U test). Kaplan-Meier survival curves with log rank tests will be used to determine a difference in graft and patient survival over time.

Safety data will include patient and graft survival, biopsy proven acute rejection, and hospital admissions.

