10.1.3 Handling of missing values/censoring/discontinuations

Patients lost to follow-up or discontinued from the study will be censored from further analysis at the time of their withdrawal from the study.

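### Hospital admissions can recur over three years, but the planned tests ignore follow-up time, so an arm that loses more follow-up can look safer

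*Combined protocol and SAP*

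**What the plan says.** Section 10.1.2 lists the safety data: "Safety data will include patient and graft survival, biopsy proven acute rejection, and hospital admissions". Survival and biopsy-proven rejection in that list are also the efficacy outcomes (3.1, 7.5.1), so admissions are the one separate safety item. Section 10.2.2 has admissions reviewed monthly together with graft and patient survival, and states no denominator.

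Other repeatable events are also collected. The Measurement/Assessments paragraph of the study design includes "Emergency Room and hospitalizations, as well as unscheduled clinic and other physician visits", and the synopsis, under Other assessments, lists "Number and grade of acute rejection episodes at 6 months, 1, 2, and 3 years after transplantation". Section 8.2 covers every serious adverse event (SAE) regardless of suspected causality, from consent until 30 days after participation ends. The study title in the synopsis promises a trial "comparing patient and graft survival, adverse events and tolerability".

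The methods in 10.1.2, repeated in 10.2.1, are "dichotomous variables evaluated by Chi-Squared analysis, continuous variables by Student's T-Test", with a Wilcoxon rank sum test for non-parametric outcomes. Only one method uses follow-up time: "Kaplan-Meier survival curves with log rank tests will be used to determine a difference in graft and patient survival over time". Under 10.1.3, patients who are lost to follow-up or discontinued are "censored from further analysis at the time of their withdrawal from the study".

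**The concern.** The plan has a censoring rule but, for admissions, no method that can apply it. A t test or Wilcoxon test on admissions per patient treats a patient seen for four months like one seen for three years. A chi-squared test on any admission does the same. A patient who leaves early has had less time to be admitted, so the arm with more early departures shows fewer admissions at the same underlying rate.

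Unequal loss is plausible here, although not documented. Section 1 says that many of the centre's patients have to stop Rapamune for side effects or because of its dosing time, and section 2 expects that patients may do better on everolimus. The glossary says that stopping study drug may or may not coincide with withdrawal from the study, and that no further assessments are planned after withdrawal. If intolerance leads to withdrawal, follow-up could differ by arm, in either direction.

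At stake is the one safety comparison in 10.1.2 and 10.2.2 that does not duplicate efficacy, and a monthly review on which the programme's directors may halt or amend the study.

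**Working it through.** **Nothing to reproduce.** The sample size of 60 comes without a calculation, and no admission rate, dropout rate or variance is stated.

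**Inputs from the documents.** 60 patients, 2:1, so 40 Zortress and 20 sirolimus (section 5); enrolment over 12 months and three years of follow-up (section 5); first-year rejection 7% to 10% at this centre (section 1).

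**Assumed inputs.** Two-sided 5% tests; 0.5 or 1.0 admissions per patient-year; Poisson counts, or gamma-Poisson counts with variance μ + kμ² and k = 1 or 2; departures spread evenly over the follow-up period.

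**Step 1: bias in counts per patient at equal true rates.** A patient who leaves contributes on average half the period. If a fraction d leaves, mean follow-up is (1 − d/2) of the full period, and at a constant rate the mean count shrinks by the same factor. The ratio between arms is (1 − d₁/2)/(1 − d₂/2).

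| Loss, arm 1 vs arm 2 | Ratio of mean counts | True ratio 1.25 against arm 1 appears as |
|---|---|---|
| 10% vs 10% | 0.95/0.95 = 1.00 | 1.25 |
| 30% vs 10% | 0.85/0.95 = 0.895 | 1.25 × 0.895 = 1.12 |
| 50% vs 10% | 0.75/0.95 = 0.789 | 1.25 × 0.789 = 0.99 |

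Dividing by person-time returns 1.00 in the first column of results and 1.25 in the second.

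**Step 2: effect on the tests.** In simulations with 40 and 20 patients and no true difference:

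- With equal loss (none, or 10% in each arm), t and Wilcoxon tests reject in about 3% to 7% of trials.
- At 30% vs 10% loss they reject in about 5% to 10%.
- At 50% vs 10%, over three years at 1.0 admission per year, they reject in about 22% (t) and 24% to 25% (Wilcoxon) with Poisson counts, against about 5% for a person-time rate test with robust variance. With k = 1 the figures are about 12%, 12% to 13%, and 7% to 8%.
- The robust rate test for admissions rejects in about 5% to 9% in most scenarios, so it is slightly liberal with 20 controls.

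**Step 3: why one offset over three years is not enough.** Suppose that the rate is 1.0 per year in year 1 and 0.5 per year afterwards (assumed). A completer expects 1.0 + 2 × 0.5 = 2 admissions. A patient who leaves at an evenly distributed time has on average 5/6 of a year in year 1 and 2/3 of a year later, so expects 5/6 + 0.5 × 2/3 = 7/6, a shortfall of 5/6. At 30% loss the mean is 2 − 0.3 × 5/6 = 1.75; at 10% it is 2 − 0.1 × 5/6 = 1.917. The count ratio is 1.75/1.917 = 0.91. With a single constant-rate offset the ratio is (1.75/2.55)/(1.917/2.85) = 1.02. The bias becomes small but changes direction. Rates within time windows avoid most of this.

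**Step 4: rejection.** 7% to 10% of 60 is 4.2 to 6 patients with a first-year rejection. That is too few for a stable rate model, and repeat episodes will be fewer still.

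**The case against.** The strongest reply is that nothing in section 10 is wrong as written. The tests are assigned by type of variable, and all can be run per patient, where error rates stay near 5% if follow-up is equal. The bias needs unequal loss, on which the documents are silent, and at 30% vs 10% the error rate hardly moves. The study is a 60-patient pilot, declared exploratory and not powered (3.2, 10.3), and wound complications, lymphocele and new-onset diabetes are analysed as well. All of this stands and limits the weight of the point. It does not supply a denominator, and a biased estimate misleads even when nobody relies on its p-value.

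Five stronger readings are tempting but not supported:

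- **That admissions will be tested as independent events, making the test too liberal.** No section makes the event the unit of analysis. The unit for repeated events is simply not stated.
- **That raw arm totals will be compared, so that 2:1 allocation alone would suggest harm from Zortress.** The stated tests compare proportions, means or ranks. Section 10.2.2 does not say how the monthly figures will be displayed, so this is a reason to specify the display, not a planned error.
- **That 10.1.3 ends follow-up at death or graft loss, so counts reward worse survival.** It mentions neither, and survival is compared directly and reviewed beside admissions.
- **That rejection counts are seriously affected.** At 7% to 10%, repeats are too few to matter.
- **That emergency visits are analysed wrongly.** They are collected, but section 10 does not list them as an endpoint.

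On SAEs, the safety list in 10.1.2 is not worded as exhaustive, and admissions and deaths already capture many SAEs. Even so, section 10 names no SAE comparison although the title promises one for adverse events.

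**Conclusion.** The point holds as a gap in specification: for admissions the plan has censoring at withdrawal, no person-time, and no stated unit of analysis. If loss is unequal, counts per patient flatter the arm with more loss by about 10% (30% vs 10%) to 21% (50% vs 10%), and in the second case a true 25% excess would vanish. With equal loss there is no bias. These sizes rest on assumed loss, a constant admission rate and evenly spread departures. Inflated test error becomes material only towards the 50% vs 10% end. The consequence is limited to safety description and monthly monitoring in an exploratory pilot, but the remedy is cheap and uses data already collected.

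**What to change.** In 10.1.2 and 10.2.2:

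1. State that the patient is the unit of analysis. Define when counting starts and ends, and whether the transplant stay itself counts as an admission.
2. Report admissions and SAEs per patient-year by arm, with a rate ratio and 95% interval from a negative binomial model, or Poisson with robust variance, with log follow-up time as offset. Do this within windows that follow the plan's own time points: 0–6 months, 6–12 months, year 2 and year 3.
3. Beside each rate give the number of patients with at least one event, and the person-time by arm.
4. Name SAEs in the safety data, with person-time matching the collection period in 8.2.
5. For rejection episodes give descriptive rates and the proportion with any episode, with no rate model.
6. In the monthly review show admissions per patient-month by arm, because allocation is 2:1 and staggered enrolment gives patients different exposure at every review.

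The cost is SAP wording and models available in SPSS or STATA. The downside is wide intervals, more so within windows, and robust tests that are slightly liberal with 20 controls. The estimates and intervals should therefore carry the interpretation rather than p-values.

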10.1.3 Handling of missing values/censoring/discontinuations

Patients lost to follow-up or discontinued from the study will be censored from further analysis at the time of their withdrawal from the study.

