- Results of 12 month surveillance biopsies
- Lipid panels and use of lipid lowering medications at 1 year after transplant
- Incidence of MI and CHF at 1 and 3 years after transplant

- Incidence of wound infection at 1 year after transplantation
- Incidence of lymphocele at 1 year after transplantation
- Plasma concentrations of S-adenosyl homocysteine (SAH) and S-adenosyl methionine (SAM) Plasma concentrations of endothelial dysfunction markers (symmetric and asymmetric dimethyl arginine (SDMA, ADMA), L-arginine, L-citrulline, L-ornithine, cysteine, and homocysteine over the observation period
- Plasma concentrations of bioactive lipids (HODEs, HEPEs, HETEs, and prostaglandins) over the observation period
- Plasma protein patterns

Data analysis: The incidence of graft loss, patient death, and acute rejection will be compared by chi squared analyses. Patient and graft Kaplan-Meier survival curves will be compared by log rank test. We hypothesize there will be no statistically significant difference between the treatment arms. As this is a pilot study, it was not statistically powered to detect subtle differences in outcome. All continuous variables such as serum creatinine, cGFR, serum lipids, WBC, platelets, etcetera will be compared by student's t test. Any other dichotomous variables will be compared by chi squared analysis.

1 Background

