8.2 Serious adverse event reporting

To ensure patient safety, every SAE, regardless of suspected causality, occurring after the patient has provided informed consent and until 30 days after the patient has stopped study participation (defined as time of last dose of study drug taken or last visit whichever is later).

Any SAEs experienced after this 30 day period should only be reported to Novartis if the investigator suspects a causal relationship to the study drug.

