10.1 Analysis of the primary objective(s)

10.1.1 Variable

The primary endpoint consists of non-death censored graft survival and biopsy proven acute rejection at 1 year post-transplant. These events will be directly measured and not calculated.

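### The censoring rule in section 10.1.3 suits the survival curves but cannot be applied in the chi-square comparison of 1-year rejection and, by inference, of the 1-year primary composite (minor)

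*Combined protocol and SAP*

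**What the plan says.** Section 10.1.3 is a single sentence: "Patients lost to follow-up or discontinued from the study will be censored from further analysis at the time of their withdrawal from the study". No other section gives an analysis set, a denominator for the 1-year comparisons, an imputation rule or a sensitivity analysis.

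Two kinds of analysis are planned for the main outcomes:

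- **Time to event.** Section 10.1.2 says "Kaplan-Meier survival curves with log rank tests will be used to determine a difference in graft and patient survival over time". Rejection and the composite are not included.
- **Fixed time point.** The synopsis (Data analysis) says "The incidence of graft loss, patient death, and acute rejection will be compared by chi squared analyses". Section 10.1.2 has "dichotomous variables evaluated by Chi-Squared analysis" as a general rule.

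The primary endpoint (sections 3.1, 10.1.1 and 10.1.2) combines graft survival, with death counted as graft loss, and biopsy-proven acute rejection, both at 1 year. It has no test of its own, so the general rule for dichotomous variables is the one that reaches it. Section 10.1.1 adds "These events will be directly measured and not calculated", which does not cover a patient whose 1-year status was never observed.

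**The concern.** A chi-square table needs a yes or a no for every patient it contains. It has no place for a patient who was event-free when censored at, say, month 5. The plan's one rule for such patients therefore has no direct meaning in the analysis that appears to carry the primary endpoint. Someone has to decide whether the patient is dropped, counted event-free or counted as an event, and that choice would be made after the data are known.

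The stakes are the two reported 1-year rates and their difference. These matter because section 3.1 aims at equivalency and section 10.5 expects non-inferiority, and both rest on the estimated difference. Few events are expected. With 60 patients randomised 2:1 (40 v 20) and the centre's 7% to 10% rejection rate from section 1, that is 2.8 to 4.0 rejections against 1.4 to 2.0.

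**Working it through.** The plan states no withdrawal rate and derives no sample size, so there is no figure of its own to reproduce. What follows is an illustration.

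**Inputs.** From the documents: 40 v 20 patients; 1-year risk p = 7% or 10% (the rejection rate in section 1; the composite risk is at least as high). Assumed: a share w = 5%, 10% or 20% would leave within the year, equally in both arms and unrelated to risk, with exponential event and leaving times.

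**Formulas.** λe = −ln(1−p) and λw = −ln(1−w).

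- Event seen before leaving: A = λe/(λe+λw) × [1 − exp(−(λe+λw))].
- Followed event-free to 1 year: S = exp(−(λe+λw)) = (1−p)(1−w).
- Unknown status: U = 1 − A − S.
- Counting leavers event-free reports A. Dropping them reports A/(A+S). Counting them as events reports A + U = 1 − S.

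**Worked case, p = 7%, w = 10%.** λe = 0.0726 and λw = 0.1054, so S = 0.93 × 0.90 = 0.837 and A = (0.0726/0.1779) × 0.163 = 0.0665. Event-free coding gives 6.65%. Dropping gives 0.0665/(0.0665 + 0.837) = 7.36%. Counting as events gives 16.3%. U = 9.65%, or about 3.9 of 40 and 1.9 of 20 patients.

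| True risk | Leaving | Counted event-free | Dropped | Kaplan-Meier target |
|---|---|---|---|---|
| 7% | 5% | 6.8% | 7.2% | 7.0% |
| 7% | 10% | 6.6% | 7.4% | 7.0% |
| 7% | 20% | 6.3% | 7.8% | 7.0% |
| 10% | 5% | 9.8% | 10.2% | 10.0% |
| 10% | 10% | 9.5% | 10.5% | 10.0% |
| 10% | 20% | 9.0% | 11.1% | 10.0% |

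**Arm difference.** In 200,000 simulated 40 v 20 trials per setting, switching between event-free coding and dropping moved the difference as follows (ranges cover the two risks).

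| Leaving | Mean shift, points | 90th percentile, points | Sign reversed, at most |
|---|---|---|---|
| 5% | 0.4 to 0.6 | 1.0 to 1.3 | 0.02% |
| 10% | 0.8 to 1.0 | 1.7 to 2.1 | 0.2% |
| 20% | 1.5 to 1.8 | 3.1 to 3.8 | 0.6% |

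**Kaplan-Meier against dropping.** At 10% leaving unrelated to risk, the root mean squared error of the arm difference is about 7.2 points for Kaplan-Meier and 7.5 for dropping at 7% risk, and 8.5 against 8.9 at 10% risk. The gain comes from keeping the leavers' follow-up. Event-free coding does not lose on this measure when the true risks are equal, because it shrinks both rates towards zero; its fault is that each arm's rate is too low.

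**If leaving is related to risk.** Suppose the hazard triples after leaving (assumed), with 10% leaving. At p = 7% the true risk is 7.65%; dropping reads 7.36% (0.3 low) and Kaplan-Meier 7.0% (0.65 low). At p = 10% the true risk is 10.90%; dropping reads 10.50% (0.4 low) and Kaplan-Meier 10.0% (0.9 low). So dropping now understates risk, and Kaplan-Meier is further off than dropping.

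**Unknown outcomes as such.** Take 3/40 v 2/20 events with 4 and 2 patients lost. Event-free coding gives 7.5% − 10.0% = −2.5 points (Zortress minus Rapamune). Dropping gives 3/36 − 2/18 = 8.3% − 11.1% = −2.8 points. The extremes are 3/40 − 4/20 = −12.5 and 7/40 − 2/20 = +7.5 points.

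**The case against.** The case against runs as follows.

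- **The rule can be read.** Censoring from further analysis at withdrawal plausibly means that an early leaver is not in a later 1-year table. This stands: dropping is the most natural reading, and what remains is partly a matter of wording. The plan nevertheless does not say so, nor whether a rejection seen before withdrawal still counts.
- **The scope is narrow.** Graft and patient survival already have Kaplan-Meier analyses, and chi-square reaches the composite only by inference. Both points are correct. The gap bites on rejection and the composite.
- **The trial is an unpowered, exploratory pilot** (sections 3.2, 10.3 and 10.4), and the shift is about 1 point. This stands, and it sets the severity.
- **Kaplan-Meier can be the worse estimate.** It can when leaving is related to risk, as the tripled-hazard case shows. Hence the sensitivity analysis in the fix.

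A reader might also infer several stronger things that the documents do not support:

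- **Each coding errs in a known direction.** That holds only if leaving is unrelated to risk.
- **The −12.5 to +7.5 point range is harm done by chi-square.** It reflects unknown outcomes in small arms and would be the same under Kaplan-Meier.
- **Patients who stop study drug are censored.** The glossary says that drug discontinuation "may or may not also be the point/time of premature patient withdrawal", and defines the end of participation as "Point/time at which the patient came in for a final evaluation visit or when study drug was discontinued whichever is later". Section 8.2 is similar ("defined as time of last dose of study drug taken or last visit whichever is later"). Section 10.1.3 censors at withdrawal from the study, and section 5 plans 3 years of follow-up.
- **Outcomes of lost patients can simply be looked up.** Section 9.1 says that patient data are kept in the centre's database. It does not say that the database holds outcomes for patients lost to follow-up.

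**Conclusion.** The mismatch is real and minor. The only missing-data rule is a censoring rule. Rejection at 1 year is sent to a test that cannot use it and, by inference, so is the primary composite. Under the natural reading the follow-up of early leavers is thrown away, and at an assumed 10% leaving a true 7% or 10% reads as 7.4% or 10.5%. The alternative codings give other rates from the same data.

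These sizes rest on assumed withdrawal rates, equal in both arms and unrelated to risk, with constant hazards. If leaving is related to risk, the direction of error is not known. Nothing here suggests that the trial's conclusion would be overturned. Confidence is high that the rule is missing and low about the size of its effect in this trial.

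**What to change.** In sections 10.1.2 and 10.1.3, state that:

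1. All randomised patients are analysed in their assigned arm.
2. The 1-year composite (biopsy-proven rejection, graft loss or death) and its risk difference are estimated by Kaplan-Meier in each arm, with a confidence interval suited to few events. The existing censoring rule applies only to withdrawal from the study or true loss to follow-up. With complete follow-up this equals the simple proportion.
3. A best-case/worst-case sensitivity analysis covers patients with unknown 1-year status, because Kaplan-Meier also assumes that leaving is uninformative.

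The interval method is optional. As a guide, in 20,000 simulated 40 v 20 trials per risk level at 10% leaving, a 95% Greenwood-Wald interval covered 92.6% (7% risk) and 91.4% (10% risk). A MOVER-Wilson interval covered 98.1% and 97.3%. Also optional are treating death and graft loss as competing events for rejection alone, and repeating in 6.5.5 or 10.1.3 that stopping study drug does not end follow-up.

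If chi-square is kept, the minimum is to say how unknown 1-year status is counted and to add items 1 and 3.

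The cost is a few sentences in the analysis section and a little more analysis work, with no new visits or patients.
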